Caudal blocks are one of the most commonly performed regional anesthetics in children and are performed daily for a host of infra-umbilical surgical procedures. A caudal block is an epidural injection, most commonly of local anesthetic into the epidural space as accessed via the sacral hiatus. In children, the sacral hiatus is a normally occurring aperture in which the epidural space may be accessed with extremely minimal risk; as neural tissue ends more proximally. Due to this measure of safety, caudal blocks are preferred in children when compared with standard lumbar epidurals. Caudal blocks are performed blindly using palpation and tactile feedback to assess if the medication is being administered in the correct location. As a result of blind injection, administration of local anesthetic totally or partially outside of the correct site can often be unnoticed or identified after a significant volume has already been injected. With the potential for toxicity of local anesthetic, this may result in either the inability to give a complete dose or an unintentional and often unnoticed sham block (incorrect site of injection).

Use of ultrasound has been proposed for identification of caudal block placement and correct medication spread. However, a recent review of the Pediatric Regional Anesthesia Network database reveals that ultrasound is reportedly only used in less than 3% of blocks. The benefit of ultrasound is safe and real-time confirmation of injection. Ultrasound allows the provider to determine with minimal local anesthetic or even saline injection if the correct space is accessed. Without ultrasound, failed blocks are either identified after significant percentage of the total dose of local anesthetic is incorrectly administered or intra or post operatively when the patient demonstrates a significant opioid requirement. This is problematic given that one of the primary benefits of a caudal block in children is the ability to avoid opioids.

Review of local practice here at Texas Children's Hospital for quality improvement purposes revealed a failure rate of caudal blocks to be 18%. Failure was defined as a heart rate increase with incision of >20% despite a caudal block and >1MAC of gas for the patient age. These patients all required opioids both intra and post operatively in addition to surgical levels of inhaled anesthetic agent.

Section D: Purpose and Objectives

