Associated procedures for which caudal does not provide complete analgesia Incarcerated hernias Emergency procedures Local Anesthetic allergy Sacral dimple Rash over sacrum precluding block Parents/legal guardians unable to consent for surgical procedure in English language Foster Care/Child protective services as guardians Parental Refusal for caudal block or study participation American Society of Anesthesiology classifications other than 1,2 or 3

F2. Procedure

Patients meeting inclusion criteria and following informed consent will be brought back to the operating room. General anesthesia will be induced in the standard manner either by inhalation induction or intravenous induction at the discretion of the anesthesia attending of record. The airway will be secured using an

age/weight appropriately sized device, at the discretion of the anesthesia attending of record. The caudal block will ensue in the same manner regardless of the study at the discretion of the anesthesia attending of record. The attending anesthesiologist will perform or instruct the placement of a caudal block according to their standard of practice. At the time of administration of local anesthetic into the caudal space, the study collaborator (SC) will ultrasound the caudal space keeping the provider placing the block blinded to the imaging. The provider placing the block will inject 0.5mL of preservative free saline. The provider will then be asked to state if they are correctly in the caudal space or not. If the provider feels they are not in the caudal space, they will re-do the procedure. If the provider fails to identify incorrect location and this is noted by ultrasound, the SC will inform the provider to re-do the procedure. After a successful injection (as confirmed by ultrasound) is performed, the patient will be prepped for the procedure in standard manner. The inhaled anesthetic will be titrated until the minimal alveolar concentration is between 0.8-1 MAC for age prior to incision. The anesthesia provider will note the heart rate immediately before and after the first surgical stimulation. Data will be recorded de-identified on the sheet (see attached). The study PI will compare MAC hours (exposure to inhaled anesthetic agent) in patients having undergone caudal block with ultrasound confirmation to those in the retrospective group gathered for quality improvement to ascertain if reduction of exposure to inhaled agent was possible.

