Section G: Sample Size/Data Analysis

G1. Sample Size

How many subjects (or specimens, or charts) will be used in this study?

Local: 150 Worldwide: 150

Please indicate why you chose the sample size proposed:

A previous study using ultrasound in children for caudal block demonstrated an incidence of 7.1% subcutaneous bulging (failed block) when ultrasound was not used. Using our primary outcome of determination of block failure rate when performing blind (without ultrasound) and assuming a difference of 20% increase in success rate would alter practice and thus be clinically significant using a one sample mean, alpha of 0.05 and a power of 80% would require an enrollment of 99 patients, each serving as their own control. Assuming a study dropout rate of 10% (unknown sacral dimple, etc.) and requirement for additional patients to perform secondary statistical analyses, 150 patients will be enrolled. Analysis performed with JMP statistical software.

G2. Data Analysis

Provide a description of your plan for data analysis. State the types of comparisons you plan (e.g. comparison of means, comparison of proportions, regressions, analysis of variance). Which is the PRIMARY comparison/analysis? How will the analyses proposed relate to the primary purposes of your study?

Data will be presented as means +/-SD, median (range) and number % when appropriate. Continuous variables will be compared with independent sample t-test or Mann-Whitney U testing for normally distributed data. Odds ratios will be noted for the primary outcome with confidence intervals displayed to achieve CI of 95%. Statistics will be aided by JMP software with P values of <0.05 considered significant.

Section H: Potential Risks/Discomforts

Describe and assess any potential risks/discomforts; (physical, psychological, social, legal, or other) and assess the likelihood and seriousness of such risks:

There are no potential risk of discomfort to the patients As with all studies, there is a small risk of loss of confidentiality or data breach.

Section I: Potential Benefits

Describe potential benefit(s) to be gained by the individual subject as a result of participating in the planned work.

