Patient: For the individual patient enrolled, there will be no deviation from the standard of practice of either the anesthetic or regional block. As nearly all providers perform this technique blindly, the patient will have the benefit of immediate recognition of incorrect block eliminating the possibility for inadvertent sham block. In addition, reduced block failure will result in less exposure to opioids and inhaled anesthetic agents.

Describe potential benefit(s) to society of the planned work.

The benefit from this study, should it show that ultrasound is superior for recognizing incorrect placement when compared with blind technique is that fewer inadvertent sham blocks may be performed. Additionally, if reduction of block failure by use of ultrasound can be established, reduced exposure to inhaled anesthetics which have potential adverse effects on neurodevelopment may be possible

Do anticipated benefits outweigh potential risks? Discuss the risk-to-benefit ratio.

The study benefits the participant that would undergo a caudal block using a blind technique in that immediate recognition of sham block would be possible allowing for correction of placement. The study would reduce the risk for patients undergoing caudal blocks with incorrect placement that provide a risk of the block with no benefit. This allows the patient to either benefit from the block or avoid wrongly placed medication should the block be aborted. As with all studies, there is a small risk of loss of confidentiality or data breach.

Section J: Consent Procedures

J1. Waiver of Consent

Will any portion of this research require a waiver of consent and authorization?

NA

J1a. Waiver of requirement for written documentation of Consent

Will this research require a waiver of the requirement for written documentation of informed consent?

NA

J2. Consent Procedures

Who will recruit subjects for this study?

PI
PI's staff

Describe how research population will be identified, recruitment procedures, any waiting period between informing the prospective participant and obtaining consent, steps taken to minimize the possibility of coercion or undue influence and consent procedures in detail.

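### Placement is judged after 0.5 mL of saline, so the primary outcome is needle position at the saline test, not a blind block failure rate or a sham-block rate

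*Combined protocol and SAP*

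**What the plan says.** F2 (Procedure) keeps the provider blinded to the image and sets the moment of judgement: "The provider placing the block will inject 0.5mL of preservative free saline. The provider will then be asked to state" whether the needle is correctly placed. A provider who thinks the needle is out repeats the block. For the remaining errors, "If the provider fails to identify incorrect location and this is noted by ultrasound, the SC will inform the provider to re-do the procedure".

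The background text before Section D describes usual blind practice differently. Injection outside the site "can often be unnoticed or identified after a significant volume has already been injected". It adds that, without ultrasound, "failed blocks are either identified after significant percentage of the total dose of local anesthetic is incorrectly administered or intra or post operatively". It treats an incomplete dose and a sham block as alternative consequences, and allows that an injection may be only partly outside the site.

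Objective 1 in Section D is the rate at which blind blocks lie outside the epidural space. G1 describes the primary outcome as the block failure rate under blind placement and treats a 20% gain in success as enough to alter practice. It takes its planning figure from a study that "demonstrated an incidence of 7.1% subcutaneous bulging (failed block) when ultrasound was not used". Section I states the benefit to society as follows: "should it show that ultrasound is superior for recognizing incorrect placement when compared with blind technique is that fewer inadvertent sham blocks may be performed".

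**The concern.** The blind technique is observed only up to the first 0.5 mL. After that the trial either discloses the error or goes on with a needle position already confirmed by ultrasound. Three different quantities are then easily run together:

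- needle position at the saline test;
- failure of the completed blind block;
- a sham block that nobody notices.

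Only the first is measured. If the result is reported under G1's label, readers will take it as the share of blind blocks that fail, and they may set it beside the 7.1% bulging figure. If it is reported in the terms of Section I, they will take it as the share of sham blocks that ultrasound would prevent. A change of practice could then rest on a number that does not estimate either.

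**Working it through.** The plan gives no sham-block rate, so there is no figure to reproduce. G1's 99 patients plays no part in this point.

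**Step 1: what can be observed.** On the first blind attempt each child falls into one of these groups:

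- A: out on ultrasound at 0.5 mL, and the provider says so. The block is re-done.
- B: out on ultrasound at 0.5 mL, and the provider says it is in. The error is disclosed and the block is re-done.
- C: in on ultrasound at 0.5 mL, and accepted. The injection proceeds.
- D: in on ultrasound at 0.5 mL, but the provider says it is out. The block is re-done.

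Objective 1, read at the saline test, is (A + B)/N. It depends on the image alone and not on when the provider would notice, so the timing of the verdict does not bias it. The rate missed by the provider is m = B/N.

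**Step 2: what cannot be observed.** Let f be the share of B that a blind provider would have recognised later in the injection. Let g be the share of all children who are in at the test but whose dose later goes partly or wholly outside, unnoticed. In usual practice:

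- unnoticed wrong-site rate = m(1 − f) + g
- missed rate minus that rate = m − [m(1 − f) + g] = mf − g

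The missed rate is too high as a sham-block rate if g < mf, and too low if g > mf. The background says late recognition occurs (f > 0) and that partly misplaced injections occur. It does not say whether the latter follow a correct test. It gives neither f nor g.

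**Step 3: scale, by assumption.** For m, I use the protocol's two failure rates purely as illustrations: 7.1% (bulging) and 18% (local review, defined by heart-rate response). Neither was measured at 0.5 mL. The values of f are assumed.

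| m | f | m(1 − f) | mf, the value of g at which the two effects cancel | mf in 150 children |
|---|---|---|---|---|
| 7.1% | 0 | 7.1% | 0 | 0 |
| 7.1% | 0.25 | 5.325% | 1.775% | 2.7 |
| 7.1% | 0.50 | 3.55% | 3.55% | 5.3 |
| 7.1% | 0.75 | 1.775% | 5.325% | 8.0 |
| 18% | 0 | 18% | 0 | 0 |
| 18% | 0.25 | 13.5% | 4.5% | 6.8 |
| 18% | 0.50 | 9.0% | 9.0% | 13.5 |
| 18% | 0.75 | 4.5% | 13.5% | 20.3 |

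With g = 0 the missed rate exceeds the sham-block rate by a factor of 1/(1 − f): 1.33 at f = 0.25, 2 at 0.50 and 4 at 0.75. With g equal to the fourth column the two agree, and beyond that the sign reverses.

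**Step 4: what the design could still add.** Group B is re-done, so no reading taken later in the trial can estimate f. Among group C, an ultrasound reading at the end of the full injection would show how often the dose ended partly or wholly outside after a correct test. F2 already places the collaborator's scan at the time local anesthetic is given.

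**The case against.** The strongest reply is that nothing planned is biased. Objective 1 is an image finding. No count of sham blocks avoided is planned in G1 or G2. Section I is a benefits statement that is conditional and says only that fewer such blocks may be performed, which can be true for any f below 1. Its stronger sentence about eliminating sham blocks concerns enrolled children whose placement is corrected. Stopping early is also the purpose of the method, since the background presents ultrasound as able to settle placement with very little injected. Most of this stands.

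A reader might go further and infer that the trial will overstate the sham blocks prevented. The documents do not support that. Late or partial misplacement after a correct test works in the opposite direction, and being asked for a verdict may itself sharpen the provider's attention; neither is quantified. The definition is also loose: the background glosses a sham block as a wrong injection site and calls it often, not always, unnoticed, so a late-recognised one is not clearly a success for the blind technique.

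A reader might also infer that the 7.1% counts errors an unaided provider would see. G1 does not say how, or by whom, the bulging was detected.

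Finally, F2's wording can be read as scanning through the injection, and the data sheet is not in the supplied text, so an end-of-injection reading may already exist.

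What the reply does not remove is G1's label. A reading at the saline test is not the failure rate of completed blind blocks, and G1 ties that label to a gain said to alter practice.

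**Conclusion.** The point holds as one of definition and interpretation. The trial measures needle placement at the 0.5 mL saline test. It does not measure the blind block failure rate that G1 names or the inadvertent sham blocks in Section I. Objective 1, as an ultrasound finding at that moment, is sound.

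The gap between the missed rate and a sham-block rate is mf − g. The documents give neither f nor g, so its direction and size are unknown. The table shows scale only and rests on assumed values of m and f. A claim of certain overstatement would go beyond the text.

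The change is modest, but it is best made before enrolment, because an end-of-injection reading that was not taken cannot be recovered at analysis.

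**What to change.** 1. In objective 1 and G1, define the primary outcome as *not in the epidural space on ultrasound at the 0.5 mL saline test*, and drop the block-failure label.
2. Report separately the misplacements that the provider did not recognise at that point.
3. In Section I and the eventual report, limit the conclusion to earlier recognition. State that the result is not a sham-block or block-failure rate and is not directly comparable with the 7.1% bulging figure.
4. If the data sheet does not already do so, record the ultrasound site at the end of the full injection (wholly in, partly out, out), and report it for blocks accepted on the first blind attempt. This serves objective 1. It also serves objective 3, which needs to know that the medication itself went to the right place. It measures late or partial misplacement only, and does not estimate how many early misses the provider would later have recognised.

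The cost is some rewording, one extra data field and a narrower claim. F2's procedure is unchanged, and the collaborator is already scanning.

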1) Identify the rate at which blindly placed caudal blocks are not within the epidural space 2) Identify the rate at which ultrasound can guide a wrong block into the correct location 3) Identify if lack of heart rate change on incision can predict successful placement when medication administration is successfully confirmed with ultrasound 4) Identify if after using ultrasound to visualize placement, if concentrations of inhaled agents may be reduced in children

Section E: Protocol Risks/Subjects

E1. Risk Category

Category 1: Research not involving greater than minimum risk.

E2. Subjects

Gender:

Both

Age:

Child (3-12 yrs), Infant/Toddler (0-36 mos)

Ethnicity:

All Ethnicities

Primary Language:

English, Spanish

Groups to be recruited will include:

Patients

Which if any of the following vulnerable populations will be recruited as subjects?

Children

Vulnerable populations require special protections. How will you obtain informed consent, protect subject confidentiality, and prevent undue coercion?

Consent will only be obtained from parents/legal guardians. Confidentiality will be maintained by the PI as no patient or provider specific identifiers will be recorded aside from consent parental signature. To avoid undue coercion, consenting parents/guardians will be informed that their willingness to participate will not affect their child's treatment course or ability to get a caudal block or have any impact on their care course.

E3. Pregnant woman/fetus

Will pregnant women and/or fetuses (as described in 45 CFR 46 Subpart B) be enrolled in the research?

No

E4. Neonates

Will neonates of uncertain viability or nonviable neonates (as described in 45 CFR 46 Subpart B) be enrolled in the research?

No

E5. Children

Will children be enrolled in the research?

Yes

Section F: Design/Procedure

F1. Design

Select one category that most adequately describes your research:

c) Pilot

Discuss the research design including but not limited to such issues as: probability of group assignment, potential for subject to be randomized to placebo group, use of control subjects, etc.

Single blinded prospective trial in which all patients serve as their own clinical control group.

Inclusion Criteria:

Children ages 0-84 months Infra-umbilical procedure for which a caudal block is already planned American Society of Anesthesiology classifications of 1,2 or 3

Exclusion Criteria:

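### The ultrasound reading behind the primary failure rate is not required to be fixed before the provider's verdict, or recorded for attempts the provider rejects

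*Combined protocol and SAP*

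**What the plan says.** The first objective in Section D is to "Identify the rate at which blindly placed caudal blocks are not within the epidural space". G1 makes the failure rate of blind placement the primary outcome. F1 describes a "Single blinded prospective trial in which all patients serve as their own clinical control group".

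F2 sets the sequence. First, "the study collaborator (SC) will ultrasound the caudal space keeping the provider placing the block blinded to the imaging". The provider then injects 0.5 mL of saline, and "The provider will then be asked to state if they are correctly in the caudal space or not". Two branches follow:

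- Provider doubts the position: "If the provider feels they are not in the caudal space, they will re-do the procedure".
- Provider does not doubt it: "If the provider fails to identify incorrect location and this is noted by ultrasound, the SC will inform the provider to re-do the procedure".

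The final injection must be confirmed by ultrasound before the child is prepared for surgery. F2 sends the data to an attached sheet, which is not part of the document text.

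The text does not say when the SC commits to a reading, whether a reading is recorded for an attempt the provider rejects, what ultrasound appearance counts as outside the space, or which attempt enters the failure rate. G1 mentions subcutaneous bulging in a previous study but does not adopt it as the criterion. G2 adds no rule on any of these points.

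**The concern.** The SC's scan is the only independent check of needle position in F2. That makes it in effect the reference standard for the first objective, although the protocol does not say so outright. The only blinding described is of the provider to the image. The SC hears the provider say 'in' or 'not in' before having to act, and on an equivocal image a reader who has heard a confident claim may lean towards it. This is review bias.

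Three results depend on an independent reading of the first attempt:

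- the primary misplacement rate;
- the comparison with blind judgement, on which Section I rests the societal benefit (ultrasound being better at recognising wrong placement);
- the second objective, whose denominator is wrong blocks. If a doubted attempt carries no recorded reading, a wrong block that the provider recognised cannot be told from a correct one that the provider doubted.

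**Working it through.** The plan gives no figure for misreading or drift, so there is none to reproduce. The sample size in G1 plays no part in this point.

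**Step 1: the four possible first attempts under F2.**

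| Ultrasound shows | Provider says | What follows | Does the text call for an SC reading of this attempt? |
|---|---|---|---|
| in | in | proceed | yes, as confirmation |
| out | in | SC calls for a redo | yes, it triggers the redo |
| out | not in | redo on the provider's opinion | not stated |
| in | not in | redo on the provider's opinion | not stated |

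The last two rows follow the same path. Without a recorded reading they look identical in the data, although only the third row is a misplacement. In the first two rows the reading is used after the provider has spoken.

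**Step 2: possible size of review bias.** Inputs:

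- p, true first-attempt misplacement: 7.1% (the figure cited in G1) or 18% (the local review in the background section). The 18% is a failure rate defined by heart-rate response, not by ultrasound, and serves only as a scenario.
- s, share of misplacements the provider recognises: 0.5 (assumption).
- f, share of correct placements the provider doubts: 0.05 (assumption).
- d, share of discordant scans on which the SC yields to the provider: 0.10 to 0.30 (assumption).

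One-way drift (the SC passes some wrong positions that the provider claimed were right): observed rate = p − p(1 − s)d.

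- p = 7.1%: 0.071 − 0.0355 × 0.10 = 6.7%; 0.071 − 0.0355 × 0.30 = 6.0%.
- p = 18%: 0.18 − 0.09 × 0.10 = 17.1%; 0.18 − 0.09 × 0.30 = 15.3%.

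Two-way drift (the SC also yields when the provider doubts a correct placement): observed rate = p − p(1 − s)d + (1 − p)fd.

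- p = 7.1%: 0.071 − 0.00355 + 0.00465 = 7.2%; 0.071 − 0.01065 + 0.01394 = 7.4%.
- p = 18%: 0.18 − 0.009 + 0.0041 = 17.5%; 0.18 − 0.027 + 0.0123 = 16.5%.

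**Step 3: effect on the comparison with blind judgement.** Unrecognised misplacement is p(1 − s). With drift it becomes p(1 − s)(1 − d).

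- p = 7.1%: 3.55% falls to 3.2% (× 0.9) or 2.5% (× 0.7).
- p = 18%: 9.0% falls to 8.1% or 6.3%.

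The relative loss equals d, 10% to 30%, whatever the values of p and s. In the overall rate one-way drift is diluted to a relative loss of (1 − s)d, here 5% to 15%.

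**Step 4: scale.** With 150 children, the exact 95% interval is 3.7% to 12.7% for 11 failures and 12.2% to 25.1% for 27. Every drifted primary rate in Step 2 lies inside the matching interval.

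**The case against.** The strongest reply is that the scan is live. F2 does not limit it to some children, and the saline goes in before the provider is asked, so an image should exist before the verdict, even on attempts that are then rejected. The two redo branches govern action, not data capture, and the final injection must be confirmed by ultrasound in any case. This stands in part. A reader might infer from the branches that self-declared misses go unscanned, and the text does not support that. But an image on a screen is not a committed reading, and confirmation of the last attempt does not supply the reading of the first.

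The data sheet may already hold an ultrasound field for each attempt, completed before the provider speaks. That cannot be excluded. The point is limited to what the protocol text requires.

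A reader might also infer a much larger distortion from counting redos. With the same assumptions, counting every redo gives p + (1 − p)f, which is 11.7% for a true 7.1% and 22.1% for a true 18%. Counting only SC-called redos gives p(1 − s), which is 3.55% and 9.0%. The protocol states neither rule, and neither fits the first objective: a doubted but correct placement is not outside the epidural space, and a recognised misplacement is. These figures show why the numerator should be written down. They do not measure an error in the plan.

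Finally, the effect of review bias on the primary rate is modest, and this is a self-described pilot. Both are true. The comparison with blind judgement is more exposed.

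**Conclusion.** The point holds as a gap in independence and recording. As F2 is written, the reader of the de facto reference hears the provider's verdict before acting, and nothing in the text requires a prior commitment or a reading of rejected attempts. Under the assumptions above, one-way drift shifts the primary rate by 0.4 to 1.1 percentage points at 7.1% and by 0.9 to 2.7 at 18%; two-way drift shifts it less. The estimate of what blind judgement misses loses 10% to 30% of its value. Recognition, doubt and drift rates have no source in the documents, so these figures show possible size only. The trial can run without the change, but a larger sample would not remove the bias, and a first-attempt reading that was not recorded may not be recoverable later. The change is worth making before enrolment.

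**What to change.** Add to F2:

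- After the 0.5 mL saline injection and before the provider is asked, the SC marks 'in' or 'out' against an ultrasound criterion written in advance. This is done for every attempt, including those then rejected.
- Neither verdict is disclosed until both are fixed.

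Add to G2:

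- Primary numerator: SC 'out' on the first attempt. Denominator: all children with a first attempt, counted once each.
- Report separately unrecognised misplacement (SC 'out', provider 'in') and false doubt (SC 'in', provider 'not in').

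The redo rules stay as they are. If the data sheet already works this way, the change is only to state the rule in the protocol.

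The cost is one extra data-sheet field, a few sentences and a brief pause at each attempt. The SC and the scan are already in the procedure. The documents do not say who completes the sheet while the SC scans, so that should be settled too.

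### Objective 4 is confounded by a protocol co-intervention: study children are brought to 0.8-1 MAC before incision, then their MAC hours are compared with a retrospective group for which no such range is stated

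*Combined protocol and SAP*

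**What the plan says.** - **Section D, objective 4:** "Identify if after using ultrasound to visualize placement, if concentrations of inhaled agents may be reduced in children".
- **F2, once the block is confirmed:** "The inhaled anesthetic will be titrated until the minimal alveolar concentration is between 0.8-1 MAC for age prior to incision". The section does not say how the agent is managed after incision.
- **F2, last sentence:** "The study PI will compare MAC hours (exposure to inhaled anesthetic agent) in patients having undergone caudal block with ultrasound confirmation", set against the comparator in the same sentence, "to those in the retrospective group gathered for quality improvement to ascertain if reduction of exposure to inhaled agent was possible".
- **Background, before Section D:** the local quality-improvement review found an 18% failure rate. "Failure was defined as a heart rate increase with incision of >20% despite a caudal block and >1MAC of gas for the patient age". Of the failed cases it adds: "These patients all required opioids both intra and post operatively in addition to surgical levels of inhaled anesthetic agent".
- **F1:** "Single blinded prospective trial in which all patients serve as their own clinical control group". There is no concurrent group without ultrasound.
- **G2:** continuous variables get an unadjusted two-sample t-test or Mann-Whitney test, with P below 0.05 called significant. No adjustment for duration, age or procedure is planned.
- **Section I:** participants' anesthetic and block are said not to depart from usual practice.

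**The concern.** Before incision, the quantity that objective 4 studies is set by the protocol. It is not observed as a response to the confirmed block. The comparison group is historical, with no stated titration range, so the two groups may differ in two ways at once: ultrasound confirmation and the concentration rule. The own-control design does not help, because each child has one anesthetic and so one MAC-hour total.

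If MAC hours come out lower in the study group, the plan's wording leads to the conclusion that ultrasound confirmation made a reduction possible. Section I links lower inhaled-agent exposure to possible neurodevelopmental benefit, so that conclusion would carry weight. The same difference could arise with no contribution from ultrasound.

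**Working it through.** The plan gives no effect size, SD or power for MAC hours, so there is no figure to reproduce. The check sets the passages side by side and then illustrates the size.

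**1. What is known about each group at incision**

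| | Study group | Retrospective group |
|---|---|---|
| Stated range before incision | 0.8-1 MAC (F2) | none stated |
| Known above 1 MAC at incision | none, if F2 is followed | at least the 18% who failed |
| Mean concentration, duration, size | not applicable yet | not given |

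The 18% entry assumes that the group in F2 is the one in the background section. Those children were above 1 MAC when the heart rate rose, so that level was not a reaction to the rise.

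**2. Formula.** Take MAC hours as concentration times time. Let *m* be the study concentration under the range, *h* the mean retrospective concentration, and *f* the share of anesthetic time that the range governs. With equal durations, equal concentration outside *f*, and no ultrasound effect:

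proportional reduction = *f* × (1 − *m*/*h*)

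**3. Illustration, with *m* = 0.9 and *h* = 1.2 assumed.** 1 − 0.9/1.2 = 0.25.

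| *f* | Artefact | Chance of P < 0.05, SD 30% of mean | Chance of P < 0.05, SD 50% of mean |
|---|---|---|---|
| 0.2 | 0.2 × 0.25 = 5% | 25% | 12% |
| 0.5 | 0.5 × 0.25 = 12.5% | 90% | 49% |
| 1.0 | 1.0 × 0.25 = 25% | 100% | 97% |

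The last two columns assume 150 study children, 100 retrospective children and a two-sided 0.05 test: chance = Φ(shift/SE − 1.96), with SE = SD × √(1/150 + 1/100). For the first row at 30%: SE = 0.30 × 0.1291 = 0.0387, 0.05/0.0387 = 1.29, Φ(−0.67) = 25%. The retrospective size and both SDs are assumptions.

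**4. Lower cases.** If only the 18% failed cases were above the range, at an assumed 1.2 MAC, and the rest ran at 0.9, then *h* = 0.18 × 1.2 + 0.82 × 0.9 = 0.954 and 1 − 0.9/0.954 = 5.7%. The artefact is then 1.1% at *f* = 0.2 and 5.7% at *f* = 1. If *h* = *m*, it is zero.

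**5. Opposite direction.** The study scan and ultrasound-prompted redos add anesthetic time. At equal average concentration otherwise, a 5% artefact is cancelled by 1/0.95 − 1 = 5.3% more time, and a 12.5% artefact by 1/0.875 − 1 = 14.3%. The documents do not give the time added.

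**The case against.** The strongest reply is that the range applies only before incision. MAC hours cover the whole anesthetic, and nothing fixes the agent after incision, when a working block could lower the requirement. Section I says the anesthetic follows usual practice, so 0.8-1 MAC may be what the retrospective children received too. This is also the last of four objectives in a declared pilot, and F2 already records heart rate around first stimulation at the stated range, which bears directly on the objective.

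Most of this stands as a limit on the point. Four stronger readings are tempting, and the documents do not support them:

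- *Objective 4 is circular.* The protocol sets the pre-incision concentration, but only part of total MAC hours.
- *The retrospective children had no titration rule.* The documents are silent. They state no range, which is not the same thing.
- *Redos lengthened anesthesia in the study group only.* Providers in the retrospective group may also have repeated blocks they judged misplaced. Only the study scan and ultrasound-prompted redos are specific to the study.
- *An assumed gap in concentration at incision measures the bias.* The outcome is MAC hours, so the gap has to be scaled by the share of time that the range governs.

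The reply does not rescue the comparison. If 0.8-1 MAC was already usual practice, the failures recorded above 1 MAC need explaining. No concurrent group or planned adjustment separates the range from the block.

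**Conclusion.** The concern holds as confounding by a co-intervention. Under the plan as written, a MAC-hour difference mixes the titration range, the confirmed block and added procedure time, and cannot be credited to ultrasound. The net direction is not determined by the documents.

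The size is unknown. On the assumed 1.2 against 0.9 MAC with equal durations it runs from 5% to 25% of MAC hours as the governed share of time goes from 20% to 100%. It is smaller if only the failed cases exceeded the range, and nil if both groups ran at the same level. The documented part is that at least 18% of the retrospective group were above the study ceiling at incision and that no equivalent range is stated for that group. The plan should be changed, but this is a secondary objective and the primary outcome is unaffected.

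**What to change.** 1. **Change the main analysis for objective 4 in G2.** Report the proportion of children with an ultrasound-confirmed block who had no heart-rate rise above 20% at first stimulation while within the F2 range, with a 95% CI. Report the same proportion among all enrolled children, including those whose block was aborted or not confirmed. F2 already collects the heart rates; check that the data sheet also records the MAC reading at that moment.
2. **Label the MAC-hour comparison descriptive.** Where records allow, report time-averaged MAC separately before and after first stimulation. Even the later window starts from the protocol level in study children, so state that any difference reflects the titration range and the confirmed block together and cannot be credited to ultrasound alone.
3. **Reconcile F2 with Section I.** Say whether the range is usual practice or a study requirement, and state how the agent was managed in the retrospective group. This is a matter of description; no new concentration rule is needed.

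**Cost:** wording in F2, G2 and Section I, and some chart extraction; retrospective charts without timed readings drop out of the split by period. The claim for objective 4 becomes narrower. A single-arm proportion shows how often the range was compatible with no heart-rate response after a confirmed block; it does not show a reduction from an earlier level.
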